8.2. Procedures for Assessing Efficacy

8.2.1. Bleeding Assessment

Bleeding assessment will commence when the participant is randomised and stopped when one of the following occurs:

- It has been 30 days since the trial treatment was commenced
- Or in those cases where trial treatment was *not* started, 30 days from platelet count $\leq 30 \times 10^9/L$ or the commencement of chemotherapy/stem cell conditioning therapy
- The participant dies.
- Participant withdraws his/her consent to having bleeding assessments performed.
- Site investigator withdraws the participant from all further study assessments.

Bleeding assessments will be conducted using a tool based upon that used in the recent TOPPS trial ([20](#)) and further developed by an international working group – the BEST collaborative ([46](#)). If a participant is an out-patient between day of randomisation and trial treatment starting they will be asked to inform the research team if they have had any bleeding at home. Simple guidance notes will be provided to assist with this.

Rates of recorded bleeding are known to vary considerably between trials. Reasons for this variability have been explored and published through a review organised by the BEST collaboration, and include different patient groups and bleeding definitions, and variable follow up periods ([39](#)).

In the TREATT trial, a number of measures will be taken to standardise documentation and recording of bleeding, including trained assessors, monitoring and education. In the recent TOPPS ([20](#)) trial, where completeness of bleeding outcome documentation was excellent, a bleeding assessment was completed on 93% (8405/9030) of days for patients in the no-prophylaxis group, and 97% (8733/8970) of days in the prophylaxis group. The majority of patients in both arms had bleeding information collected on each trial day (median no-prophylaxis 30 days (IQR 29 to 30); median prophylaxis 30 days (IQR 30 to 30)).

For inpatients, bleeding assessments will be performed using the bleeding assessment tool which includes a physical assessment of the participant, patient interview (if possible) and review of patient chart and laboratory data. Research staff will perform the physical assessment and interview before reviewing the participant's charts, medical notes and

laboratory data to allow an objective assessment. Research staff will perform the bleeding assessment at approximately the same time each day.

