#### 1.5.2 Primary efficacy outcomes

616 participants will be accrued to the UK/Australian clinical trial.

The participants will be randomised in a double blind fashion to receive TXA or a matching placebo.

The clinical trial will be conducted with the primary endpoint of decreased proportion of death or WHO Grade 2 or higher bleeding among all participants receiving TXA versus placebo over 30 days. The type 1 error will be controlled at a two-sided level of 0.05. The primary endpoint will be analysed using the Kaplan-Meier (KM) method to estimate the probability of bleeding or death within 30 days in the analysis populations. Power and sample size calculations are based on a log-rank test for comparing two survival curves, as described in Collett.

It is anticipated that the UK and Australia will be able to recruit 616 participants for this trial. Under the assumption that anti-fibrinolysis results in a decrease of death or WHO Grade 2 bleeding from 43% to 32%, the 616 participants will provide 80% power to detect an observed absolute decrease in bleeding rates of 11% (a relative reduction of 26% with a NNT of 8.9) and will be judged statistically significant at the two-sided 0.05 level. The planned trial size of 616 subjects includes an additional 5% of participants above the required sample size of 586. This 5% figure is more than the proportion of participants within TOPPS (4%) that dropped their platelet count below  $50 \times 10^9/L$  but did not drop their platelet below  $30 \times 10^9/L$ . This therefore accounts for the number of participants within the trial who are randomised but never receive the trial treatment.

We do not expect there to be a problem with the assessment of the primary outcome of bleeding over the 30 day trial period, starting from the first day of administration of the study intervention. In the recent TOPPS trial, completeness of bleeding outcome documentation was

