### 4.3 Analysis of primary outcome measures

#### **Primary efficacy analysis**

The proportion of participants who die or have bleeding of grade 2 or above by WHO criteria during the first 30 days from the day the first dose of trial treatment is administered, will be estimated by the Kaplan-Meier method and compared by treatment arm using Cox regression analysis. All participants whose platelet count dropped to  $30 \times 10^9/L$  or below, regardless of length of follow-up will be included. Participants withdrawn or lost to follow up before day 30 will be censored at the time that they withdrew/were lost to follow up. Any missing bleeding assessments during the 30-day follow up period or to the last point of contact, whichever is first, will be assumed to be grade 1 or below.

If there is evidence of a difference in the primary outcome between treatment arms, the number needed to treat (NNT) (for benefit) will be presented. NNT is the number of participants who need to be treated with tranexamic acid in addition to standard care in order for one additional participant to benefit. It is calculated as  $1 / (\text{difference in proportion experiencing the primary outcome in each treatment arm as a decimal})$ .

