### 4.8 Procedures for handling Missing Data

For all outcomes, the volume of missing data will be summarised by treatment arm.

Participants withdrawn or lost to follow up before day 30 will be included in the primary outcome analysis (and in secondary outcome analyses where possible), censoring at the time that they withdrew/were lost to follow up.

It is expected that deaths and other safety outcomes, other than for participants withdrawn or lost to follow up, will be fully reported.

For the main analysis of the primary outcome, any missing bleeding assessments during the 30-day follow up period or to the last point of contact, whichever is first, will be assumed to be grade 1 or below. Sensitivity of the primary outcome to missing data will be assessed as per the sensitivity analysis described above.

Missing values for secondary and baseline characteristics will not be imputed. Missing data will be excluded from the relevant analyses.

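### A participant who stops only the bleeding assessments can be carried to day 30 as free of a grade 2+ bleed; the SAP should say that such a participant is censored

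*SAP*

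**What the plan says.** SAP 4.3 estimates the 30-day proportion with death or WHO grade 2+ bleeding by Kaplan-Meier and compares arms by Cox regression. It has two rules for incomplete data:

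- Participants withdrawn or lost to follow-up before day 30 are censored at that time.
- For all others, the missing days are filled with a bleed no worse than grade 1: "Any missing bleeding assessments during the 30-day follow up period or to the last point of contact, whichever is first, will be assumed". SAP 4.8 repeats this rule: "any missing bleeding assessments during the 30-day follow up period or to the last point of contact, whichever is first, will be assumed".

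Protocol 8.2.1 lists the reasons for ending bleeding assessments. One is "Participant withdraws his/her consent to having bleeding assessments performed". It stands apart from death and from withdrawal by the site investigator. Protocol 6.2.6 keeps participants in follow-up unless they withdraw consent from all stages of the trial.

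SAP 4.7 plans a sensitivity analysis that multiply imputes every missing assessment up to day 30, with its own results table in 5.9. The primary outcome table in 5.4 reports missing assessments by arm.

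**The concern.** Read together, these sections leave one group without a stated rule. A participant who declines further bleeding assessments but stays in the trial is not clearly withdrawn, is not lost, and may have a last contact on or after day 30. The second rule then fills the unassessed days with no qualifying bleed, and the participant stays in the risk set to day 30. Someone assessed only to day 5 can enter the primary estimate as a complete 30-day non-event. A later death would still count.

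Protocol 7.1 chose a time-to-event analysis so that people with incomplete follow-up could contribute until their information ends. Filling the days in gives up that advantage for this group and replaces an unknown bleeding risk with zero. At stake are the two absolute proportions, the risk difference and the NNT, which are headline outputs in SAP 5.4. The treatment comparison is at stake only if stopping differs between arms.

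**Working it through.** **Inputs from SAP 1.5.2**
- "The type 1 error will be controlled at a two-sided level of 0.05"; 80% power; "anti-fibrinolysis results in a decrease of death or WHO Grade 2 bleeding from 43% to 32" per cent.
- "Power and sample size calculations are based on a log-rank test for comparing two survival curves".
- The total of 616 "includes an additional 5% of participants above the required sample size of 586". That addition covers people randomised but never treated, not missing assessments.
- Assessment days completed in the earlier platelet-prophylaxis trial (TOPPS): 8405/9030 and 8733/8970. Missing days are therefore 6.9% and 2.6% by arm, and 1 − 17138/18000 = 4.8% overall.

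**The plan's own figure**
- HR = ln(0.68)/ln(0.57) = 0.686.
- Schoenfeld events = 4(1.960 + 0.842)²/(ln 0.686)² = 221.2.
- N = 221.2/0.375 = 590, against the stated 586. The sample size is reproduced closely and is not in question.
- Power at 586 (219.8 expected events) is 79.7%.

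**Effect of the rule**

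Assume a constant hazard, and that a share m of each arm stops assessments at a uniform time over days 0 to 30 but stays in contact. With p the true 30-day rate and L = −ln(1 − p), a stopper's event is seen with probability 1 − p/L. The estimate under the rule is

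p* = (1 − m)p + m(1 − p/L).

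- Placebo: p = 0.43, L = 0.562, 1 − p/L = 0.235.
- TXA: p = 0.32, L = 0.386, 1 − p/L = 0.170.

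The documents do not give m. Under uniform stopping each stopper misses half the days on average. If every missing day in the earlier trial had come from such stoppers, m = 0.048/0.5 = 9.6%.

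| m (assumed) | Placebo | TXA | Risk difference | NNT | HR | Power, N = 586 |
|---|---|---|---|---|---|---|
| 0 | 43.0% | 32.0% | 11.0 | 9.1 | 0.686 | 79.7% |
| 5% | 42.0% | 31.3% | 10.8 | 9.3 | 0.687 | 78.4% |
| 9.6% | 41.1% | 30.6% | 10.6 | 9.5 | 0.688 | 77.2% |
| 20% | 39.1% | 29.0% | 10.1 | 9.9 | 0.691 | 74.3% |

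(NNT here is 1/0.11 = 9.1 at m = 0. The plan's 8.9 comes from 26% of 43%.)

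Simulated Kaplan-Meier curves with 200,000 per arm agree. At m = 9.6% the rule gives 41.1% and 30.4%; censoring at the last assessment gives 43.0% and 31.8%. Putting the same 4.8% of missing days into people who stop at once gives 0.43 × 0.952 = 40.9% and 0.32 × 0.952 = 30.5%, so the result depends little on the uniform assumption.

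**How much of the power loss is due to the rule**

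Both rules observe the same bleeds. At m = 9.6%, events = 293 × (0.4113 + 0.3056) = 210. With the HR held at 0.686, power is Φ(√210 × 0.3768/2 − 1.960) = 77.9%. So of the fall from 79.7% to 77.2%, about 1.8 points come from bleeds nobody recorded, which censoring cannot recover, and about 0.7 from the rule.

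**Unequal stopping, no true effect (43% in both arms)**
- Doubling the earlier trial's missing-day shares gives 5.3% and 13.8% stopping. With the larger share on TXA: 42.0% v 40.3%, a false difference of 1.7 points, apparent HR 0.95.
- 10% on TXA only: 43.0% v 41.1%, apparent HR 0.94.
- For scale, the standard error of the risk difference at 293 per arm is √(2 × 0.43 × 0.57/293) = 4.1 points.

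**The case against.** **The plan tests its own assumption.** The imputation in SAP 4.7 covers this case and missingness is reported by arm. This stands as a safeguard. It does not alter the primary estimate, and it does not say who is censored.

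**The documents do not say that assessment-only withdrawers go uncensored.** The withdrawals table in SAP 5.2.2 has a column for stage of withdrawal, so partial withdrawals may be recorded there. Days after assessments are stopped might also be regarded as not due, rather than missing. Forms 17a and 17b (days 60 and 120) are required only of those who completed the previous stage. This also stands: the point is a gap that permits the outcome, not a rule that orders it.

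**A reader might infer that any unreturned diary becomes a false non-event.** The documents do not support that. Outpatients who bleed are asked to consult their team, significant bleeding leads to a formal assessment, and participants at home are contacted at day 30 (Protocol 8.2.1 and 11.5.4). Their bleeding status may be known without the diary.

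**A reader might also infer a biased treatment effect.** With equal stopping the HR is almost unchanged and the risk difference shrinks slightly towards zero. Unequal stopping is possible but speculative: the trial is double-blind with matched placebo, and Protocol 8.5 continues follow-up for all outcomes in those who stop treatment, so poor tolerability need not end bleeding assessments.

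**Censoring has its own assumption**, that stopping is unrelated to bleeding risk. True, but it is weaker than assuming no qualifying bleed, and the imputation remains as a check.

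**Conclusion.** The concern holds as a gap in the primary censoring rule. Followed as written, SAP 4.3 and 4.8 can carry a participant who has stopped bleeding assessments to day 30 as free of a grade 2+ bleed. That lowers both proportions and the risk difference and raises the NNT.

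The size is modest at the earlier trial's completeness: about 1.9 points on placebo, 1.4 on TXA and 0.4 on the risk difference. These figures rest on a constant hazard, uniform and non-informative stopping, and all of the 4.8% missing days coming from early stoppers who remain in contact. They are an upper figure on that basis. Scattered missed days, stopping after platelet recovery, and deaths that still count after assessments stop would each make the effect smaller. A higher stopping rate than the earlier trial implies would make it larger.

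The documents do not support a claim that the hazard ratio or the test is materially biased. That would need stopping to differ by arm, and even the earlier trial's imbalance would produce a false difference of less than half a standard error. The change is still worth making, because it is cheap and settles an ambiguity in the primary analysis before results are seen.

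**What to change.** In SAP 4.3 and 4.8:

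1. State that a participant who permanently stops bleeding assessments before day 30, including by withdrawing consent to assessments only, is censored at the last completed assessment whatever the later vital status.
2. Keep the grade 1 or below assumption for gaps followed by a later completed assessment, and for outpatients whose bleeding status was confirmed at the day-30 contact.
3. Report deaths after such censoring in the all-cause mortality analysis, and count them as events in a sensitivity analysis. In that analysis survivors should stay at risk to day 30 as well, which is what the present rule does. Counting later deaths in the primary Kaplan-Meier estimate while censoring survivors would remove only the survivors from the risk set, and is not coherent.

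The cost is a few lines of SAP text and no new data. Slightly fewer participants are at risk late in follow-up, and a few deaths may leave the primary composite (the earlier trial had 6 deaths, 1%). The estimate relies on non-informative stopping, which the planned imputation analysis already checks.

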### 4.4 Analysis of secondary outcome measures

#### **Secondary efficacy outcomes**

- Proportion of days with bleeding up to study day 30 will be compared by treatment arm using binary logistic regression analysis (bleeding or not on any given day). Correlation at participant level will be accounted for by including a random participant effect.
- Time to first episode of bleeding of WHO grade 2 or greater up to study day 30 will be estimated using the cumulative incidence function, with the competing risk of death prior to bleeding of WHO grade 2 or greater. Median, IQR will be reported by treatment arm. To accommodate a random centre effect, Cox regression analysis will be used to compare time to first episode of bleeding of WHO grade 2 or greater between treatment arms. Participants who have not experienced bleeding of WHO grade 2 or greater will be censored at day 30 or at the point of last contact, whichever is first. Participants who died prior to study day 30 and did not experience bleeding of WHO grade 2 or greater will be censored at the time of death. The estimate of the hazard of bleeding of WHO grade 2 or greater from this model should be interpreted with caution because it does not properly account for the competing risk of death. However, since the number of deaths are predicted to be small, the impact of the competing risk is likely to be negligible. This will be explored by examining the cumulative incidence function for death prior to bleeding of WHO grade 2 or greater.
- Highest grade of bleeding up to study day 30 will be compared by treatment arm using an ordinal logistic regression model, modelling grade as an ordinal categorical outcome.
- Number of platelet transfusions/participant up to study day 30 will be compared by treatment arm using a negative binomial model. The model will include an offset to account for the number of days the participant spent in hospital, up to 30 days or to the last point of contact, whichever is first. In addition, unadjusted median, IQR number of platelet transfusions per day in hospital will be reported.
- Number of red cell transfusions/participant up to study day 30 will be compared by treatment arm using a negative binomial model. The model will include an offset to account for the number of days the participant spent in hospital, up to 30 days. In addition,

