	
Trial treatment will be started as per randomisation assignment. Either as soon as possible within 24 hours, and no later than 72 hours, of the first recorded platelet count $\leq 30 \times 10^9/L$, OR if the participant was admitted with a platelet count already below $30 \times 10^9/L$ as soon as possible within 24 hours, and no later than 72 hours after the start of chemotherapy or conditioning for a stem cell transplant.
 
All participants will start with Intravenous administration
 
The trial treatment (Tranexamic acid 1g/placebo) will be administered intravenously as a slow IV bolus over 10 minutes every 8 hours.
 
If the participant is well enough they can switch to:
 
Oral administration
 
The trial treatment (Tranexamic acid 1.5g/placebo) will be administered orally as 3 X 500mg tablets every 8 hours.

Trial hypothesis	
The hypothesis is that in patients with haematological malignancies, during a period of severe thrombocytopenia, prophylactic use of antifibrinolytics will decrease bleeding or death and the demand for platelet transfusions.

Primary outcome measure(s)	
Primary Outcome
 
Estimated proportion of participants who died or had bleeding of WHO grade 2 or above during the first 30 days of the trial. Starting from the first administration of trial treatment

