1.7. Specific objectives or hypotheses

The hypothesis is that in patients with haematological malignancies, during a period of severe thrombocytopenia, prophylactic use of antifibrinolytics would decrease bleeding and the demand for platelet transfusions. There may also be additional benefits for patients such as improved quality of life during their in-patient stay and earlier discharge home. Given the importance of understanding the cost-effectiveness of new treatments, this trial proposal will also incorporate a health economic analysis.

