6.1. Introduction

This trial has an intervention arm and a control arm. These are described in the sections below.

Trial treatment will be started as per randomisation assignment as soon as possible within 24 hours, and no later than 72 hours, of the first recorded platelet count $\leq 30 \times 10^9/L$, or if the participant was admitted with a platelet count already below $30 \times 10^9/L$ as soon as possible within 24 hours, and no later than 72 hours, after the start of chemotherapy or conditioning for a stem cell transplant

The participant's eligibility criteria MUST be rechecked to ensure they are still eligible prior to first administration of the trial treatment.

The period of time between randomisation and initiation of the trial treatment will allow time for pharmacy to prepare and dispense the trial treatment.

During their inpatient stay haematology patients may experience severe nausea and vomiting, diarrhoea, or significant mucositis. This may impair their ability to tolerate or absorb an orally administered medication. Therefore the trial treatment will initially be given by intravenous administration until the participant is well and able to tolerate the oral medication. The treating physician can then switch the medication to its oral formulation. The date on which the participant is switched from IV to oral formulation will be documented. The participant must receive at least one dose of the IV formulation before transferring to oral. Participants can return to IV after commencing oral IMP, this must be documented, but care must be taken to ensure the correct dose is prescribed.

If the participant has not met the stopping criteria when they are ready for discharge oral IMP should be prescribed.

In other patient groups the dose of tranexamic acid is the same whether it is given therapeutically or prophylactically. Due to differences in bioavailability 1g IV is equivalent to 1.5g PO. This dose is similar to the doses given in the three previous RCTs that have been performed (See Investigator Brochure for further information).

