All participants who are discharged home before completion of the trial study period (30 days from commencement of the trial treatment) will be asked to complete a daily diary. Participants will be provided with clear guidance notes to assist them in self-assessment of bleeding. They will be asked to respond with a yes/no answer as to whether they have experienced any bleeding on that day.

If a participant reports no bleeding on their bleeding diary this will be recorded as a WHO grade 0 bleed. If the participant does report bleeding they are asked to consult with their haematology care team. If the clinical team consider the bleeding to be significant then the participant should be reviewed and a bleeding assessment will be conducted by a member of the research team. If the haematology team considers the bleeding to be clinically insignificant, this will be recorded as WHO grade 1

Additionally, all participants at home will be contacted by the local research staff on day 30 from first dose of the trial treatment to review the diary and confirm arrangements to collect all completed forms, which will be forwarded on to the data manager for entry into the trial database.

Local research staff completing the daily assessments will receive training and have guide notes to help them collect these data.

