8.4. Other Measurements

The following data will be collected:

Demographics and Medical History

This will include:

- Weight

- Height
- Date of birth
- Gender
- Ethnic origin
- Diagnosis (disease and type or treatment: i.e. chemotherapy or type of stem cell transplant)
- If receiving allogeneic transplant, whether HLA matched or mismatched
- Type and date of transplant or first day of other treatment
- Previous co-morbidities
- Renal impairment
- Previous fungal infection

Laboratory Studies (All study centres)

- Urine dipstick (at enrolment)
- Haemoglobin and platelet count, required daily when participant is an in-patient and 3 times a week, or as Standard of Care, when participant is an out-patient
- Coagulation profile (PT or INR), at randomisation.
- Serum creatinine (required at enrolment, randomisation, study days 1&2, and then 3 times a week on Monday, Wednesday and Friday, or as SOC, when participant is on trial treatment)
- Liver function tests including bilirubin and albumin required if VOD suspected / reported three times a week
- HLA antibody screen - required at enrolment, and repeated if a participant develops platelet refractoriness (defined as two sequential transfusions with a 24 hour platelet increment $<5 \times 10^9/L$)

Laboratory Studies (Selected study centres)

- Fibrinolysis assay (central/local lab) – sub-study
- C-reactive protein (CRP) (this is required daily when participant is an in-patient if it is measured routinely at the participating hospital)
- Immature platelet fraction (this is required daily when participant is an in-patient and at least 3 times per week, when participant is an out-patient)

Transfusions given during study (from enrolment to study day 30)

- Data on platelet, granulocyte or stem cell transfusion
 - Reason for transfusion (prophylaxis, invasive procedure, active bleeding, risk of significant bleeding, other)
- Data on red cell transfusions
 - Number of units transfused
 - Reason for transfusion (anaemia, active bleeding, other)

Fever

- Highest temperature within each 24 hour period (defined as 8am to 8am) when participant is an inpatient

Quality of Life Assessment

- Quality of life assessment (EQ5D & FACT-Th) at randomisation, day 12 (± 2) and day 30 (± 2). EQ-5D at day 120 (± 7).

Health economic analysis (from study day 1 to study day 120)

- Number of hospital admissions, and duration of stay
- Number of ITU admissions and duration of stay
- Number of day unit admissions

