### 2.2 Secondary outcome measures

#### 2.2.1 Secondary Efficacy Outcomes

All measured during first 30 days of the trial, i.e. **from the first day of administration of the study intervention.**

- Proportion of days with bleeding (WHO grade 2 or above)
- Time to first episode of bleeding of WHO grade 2 or greater for those participants who bled
- Highest grade of bleeding a participant experiences
- Number of platelet transfusions/participant
- Number of red cell transfusions/participant
- Proportion of participants surviving up to 30 days without a platelet transfusion
- Proportion of participants surviving up to 30 days without a red cell transfusion
- Quality of life

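### The only between-arm estimate planned for transfusions per participant is a rate per hospital day, which departs from the named outcome if hospital stay differs by arm

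*SAP*

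**What the plan says.** SAP 2.2.1 lists "Number of platelet transfusions/participant" and its red cell equivalent as secondary efficacy outcomes, measured over the first 30 days from the first day of trial treatment. For each product, SAP 4.4 compares the arms with a negative binomial model: "The model will include an offset to account for the number of days the participant spent in hospital", capped at 30 days. Protocol 11.5.1 specifies the same offset. SAP 4.4 also promises unadjusted medians per day in hospital. The table shell in SAP 5.5 instead shows medians per participant, followed by a rate ratio with no stated denominator.

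Four other places bear on this:

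- **Hypothesis (Protocol synopsis):** "prophylactic use of antifibrinolytics will decrease bleeding or death and the demand for platelet transfusions".
- **Possible effect on stay (Protocol 1.7):** "There may also be additional benefits for patients such as improved quality of life during their in-patient stay and earlier discharge home".
- **Discharge before day 30:** Protocol 6.1 says "If the participant has not met the stopping criteria when they are ready for discharge oral IMP should be prescribed", and Protocol 8.2.1 makes diary arrangements for "All participants who are discharged home before completion of the trial study period".
- **Data collection:** Protocol 8.4 collects transfusions from enrolment to study day 30, and Form 10 in SAP 3.1 covers day R to study day 30. Neither is limited to in-patient days.

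**The concern.** With a log link and an offset of log(hospital days), the exponentiated treatment coefficient is a ratio of transfusions per hospital day. The named outcome is a count per participant over a fixed window. The two agree only if hospital days are balanced between arms.

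Hospital days are a post-randomisation quantity that the protocol itself says treatment may change. If TXA brings earlier discharge, the offset removes any saving in transfusions that comes through the shorter stay. It also divides all transfusions to day 30 by only some of the days on which they can be given. Elsewhere the plan names the denominator when it wants a rate: fever is per day in hospital, and thrombotic events are per day at risk. The transfusion outcomes are named per participant.

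At stake is whether the trial can answer its own question about demand for platelet transfusions. In the planned table the ratio sits directly under per-participant medians, so it would naturally be read as the contrast for that count. None of the SAP section 5 shells available for review shows hospital days by arm.

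**Working it through.** The plan states no expected transfusion count, dispersion, length of stay or target ratio, so there is no planned figure to reproduce.

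**Step 1: the relation.** Planned ratio ≈ (count ratio) / (ratio of mean hospital days), TXA versus placebo.

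- True count ratio 0.85: equal stay gives 0.85; 0.85/0.95 = 0.895; 0.85/0.90 = 0.944; 0.85/1.05 = 0.810.
- No effect on the count: 1/0.95 = 1.053; 1/0.90 = 1.111.

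**Step 2: simulation.** The only input from the documents is 293 per arm (586/2, the required size in SAP 1.5.2). The rest is assumed:

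- control mean of 6 transfusions, with dispersion 0.4, 0.6 or 0.8;
- stay normal with mean 22 and SD 5, limited to 3–30 days, then multiplied by the stay ratio;
- count either independent of, or proportional to, the participant's own stay;
- full 30-day observation and no site effect.

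Both offsets were fitted to the same data, with 1,000 replicates per cell and a two-sided likelihood-ratio test at 0.05. Ranges cover the six combinations of dispersion and count–stay relation. Monte Carlo standard error is at most 1.6 percentage points.

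| Count ratio | Stay ratio | Hospital-day ratio | Hospital-day rejection | Observation-time rejection |
|---|---|---|---|---|
| 0.85 | 1.00 | 0.849–0.853 | 49.2–71.8% | 46.0–72.0% |
| 0.85 | 0.95 | 0.894–0.898 | 24.3–41.4% | 46.0–72.0% |
| 0.85 | 0.90 | 0.943–0.948 | 9.0–15.6% | 46.0–72.0% |
| 0.85 | 1.05 | 0.808–0.812 | 70.6–92.0% | 46.0–72.0% |
| 1.00 | 1.00 | – | 4.4–6.2% | 4.8–6.7% |
| 1.00 | 0.95 | 1.051–1.056 | 10.0–13.2% | 4.8–6.7% |
| 1.00 | 0.90 | 1.109–1.115 | 24.8–38.0% | 4.8–6.7% |

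The observation-time model returned about 0.85 or 1.00 throughout. Shortening stay by 5% or 10% in both arms gave the same result as equal stay, so it is the difference between arms that matters.

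**Step 3: the reverse case.** Suppose the daily transfusion rate is identical in both arms and TXA stay is 10% shorter. Under the same assumptions (500 replicates per cell), the hospital-day model reads about 1.00 and rejects in 4–7% of trials. The observation-time model reads about 0.90 and rejects in 24–37%. With stay 5% shorter, the rejection rates are about 4% and 9–14%. Here use per participant really falls, wholly through shorter stay, and the planned ratio does not show it.

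**Step 4: is observation time a safer denominator?** It too arises after randomisation, but it should be near 30 days for almost everyone: SAP 1.5.2 cites 6 deaths (1%) in TOPPS. As an assumed bad case, let 5% of one arm be observed for only 15 of 30 days and nobody be lost in the other. Mean observed days then differ by 0.05 × 15/30 = 2.5%.

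**The case against.** The strongest reply is that this is an open, prespecified choice on which protocol and SAP agree. A per-hospital-day rate has a rationale: prophylactic platelets follow a recorded count, and Protocol 8.4 says counts are "required daily when participant is an in-patient and 3 times a week, or as Standard of Care, when participant is an out-patient". On this view, preferring observation time is only a preference between estimands. That stands as a reason to keep the hospital-day model, but it does not supply a comparison of the outcome as named.

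Second, the problem needs stay to differ by arm. The only support is one tentative sentence in Protocol 1.7, and length of stay is not a listed outcome. That is right, and it is why no likely size can be given.

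Third, the rejection rates in Step 2 with no effect on the count are not false positives for the planned quantity, because the rate per hospital day truly differs there. Likewise, the two power figures test different hypotheses. Both points are correct: the table shows how far the planned ratio can mislead about the count, not that the model is invalid.

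Fourth, other results help. Per-participant medians, the promised per-hospital-day medians, hazard ratios for transfusion-free survival and the UK-only cost comparison in Protocol 12.2 all bear on transfusion use. A careful reader with both sets of medians could roughly sense a difference in stay, although the shell omits the second set. None of these gives a between-arm estimate for the count.

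Finally, an added model means one more contrast per product in a plan without multiplicity adjustment (SAP 4.2). That is a small cost, provided each ratio is labelled.

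**Conclusion.** The concern holds. The plan names a count per participant, and its only between-arm estimate for that count is a rate per hospital day. The departure is nil if stay is balanced. If stay is 5–10% shorter on TXA, a true 15% reduction reads as about 11% (ratio 0.895) or 6% (0.944), and no effect reads as a 5–11% increase. If stay is longer on TXA, the error runs the other way.

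The ratio relation is approximate but matched the simulated values closely. The power and rejection figures rest on assumed counts, dispersion and stay, and serve only as illustration. Harm is limited to secondary outcomes. It should be fixed because platelet demand is in the trial hypothesis and the remedy is cheap.

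**What to change.** Before unblinding, amend the SAP as follows:

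1. For each product, add one negative binomial model with offset log(days under observation), counted from day 1 (or planned day 1 if untreated) to the earliest of day 30, death, withdrawal or last contact. Use the SAP 4.2 site random effect. Report this as the rate ratio for transfusions per participant.
2. Apply the same end rule to both products. At present the platelet offset in SAP 4.4 stops at last contact, and the red cell offset does not say so.
3. Keep the prespecified hospital-day model, label it as per day in hospital, and state how a participant with zero hospital days is handled, since the log offset is then undefined.
4. In the SAP 5.5 table, give the denominator of each ratio, include the per-hospital-day medians already promised, and add a row for hospital days to day 30 by arm.
5. If the ratio reported first changes, document that as a departure from Protocol 11.5.1.

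The cost is one extra model per product, a few table entries and a short amendment. Duration of stay is already collected (Protocol 8.4), and times of death, withdrawal and loss are already needed for transfusion-free survival (SAP 4.4).
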